2.2 INVESTIGATION OBJECTIVES

The primary objective of this investigation is to demonstrate the effectiveness of the SIFS in a lumbar interbody application. Effectiveness will be determined as a composite score that represents patient success. To be considered a patient success, each of the following criteria must be met at the 24-month study interval:

- Pain – Improvement in low back pain score evidenced by a 20 mm reduction on a 100 mm Visual Analog Scale (VAS) when compared to baseline (Note: a lower VAS pain score indicates less pain),
- Function – Improvement in low back function evidenced by a 15 point decrease of the Oswestry Disability Index (ODI) score compared to baseline. (Note: a higher ODI score indicates a greater disability with respect to low back function),
- Fusion – Bridging bone demonstrated on CT Scan
- Safety – Freedom from device-related Serious Adverse Events and secondary surgical interventions at the index level through the 24-month study interval.

In addition to the above stated primary objective, this investigation will yield data on the following outcomes, subject parameters and clinical utility:

- Variable scores over time (pain, function, fusion) as individual parameters
- Adverse Event rate(s) reported by relatedness and severity
- Neurological status over time
- Quantitative/qualitative radiographic data over time specific to the index level and contiguous levels (translation, angulation, disc height, and device position)
- Demographics
- Hospitalization Utility (duration of surgery, estimated blood loss and duration of hospitalization)
- Work status over time
- Pain medication use

Data collection is not limited to the above data points. Additional parameters will be reported on as appropriate. For a more detailed list of supplemental outcomes refer to Section 3.2 Scientific Soundness and Statistical Analysis.

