3.0 INVESTIGATION DESIGN

3.1 OVERVIEW AND GENERAL DESIGN

This is a FDA regulated, prospective, non-randomized, single treatment arm, multicenter, IRB approved performance goal investigation designed to evaluate the safety and effectiveness of the SIFS mesh device when implanted in the intervertebral body disc space with bone graft during an instrumented lumbar fusion procedure. Enrolled subjects will be evaluated for device safety and effectiveness outcomes that support primary endpoint analysis through the 24-month time point. As previously noted in the protocol, study subjects will be expected to complete a self-administered survey annually through a maximum of 48 months post-operative as necessary until the last study subject has concluded study participation. Data from this investigation will be used to support a regulatory submission (e.g., *De novo* petition).

This non-randomized investigation will examine the primary endpoint and numerous additional outcomes. A Data Monitoring Committee will be established for this trial and shall oversee trial conduct to ensure the safety and protection of study participant rights and welfare. An independent core lab will be utilized to perform fusion assessments and radiologic measurements.

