3.2.1 Primary Endpoint

The primary endpoint (success) is a composite endpoint of pain, function, fusion, and safety, defined as meeting each of the following criteria at the 24-month study interval:

- Pain – Improvement in low back pain score evidenced by a 20 mm reduction on a 100 mm Visual Analog Scale (VAS) when compared to baseline (Note: a lower VAS pain score indicates less pain),
- Function – Improvement in low back function evidenced by a 15 point decrease of the Oswestry Disability Index (ODI) score compared to baseline. (Note: a higher ODI score indicates a greater disability with respect to low back function),
- Fusion – Bridging bone demonstrated on CT Scan
- Safety – Freedom from investigational device-related Serious Adverse Events at the index level through the 24-month study interval.

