3.2.7 Analysis of Additional Outcomes

The additional outcomes for this study are as follows:

- Mean low back VAS pain score over time through the 24-month interval
- Mean lower extremity (right and left leg) VAS scores over time through the 24-month interval
- Mean ODI score over time through the 24-month interval
- Fusion at the 12-month and the 24-month interval
- Occurrence of device-related Serious Adverse Events through the 24-month interval
- Occurrence of study-related Adverse Events through the 24-month interval
- Neurological status assessment (strength, sensation, and reflexes) over time through the 24-month interval (reporting categorized as improved, maintained, or reduced with new or increased neurological deficit being further categorized as transient (< 3 months/90 days) or longer term \geq 3 months/90 days);

- Radiographic data observed over time specific to the index level (translation, angulation, disc height, and device position)
- Subject satisfaction with procedure/outcome
- Work status over time
- Pain medication use over time
- Operative time
- Estimated blood loss
- Duration of hospitalization
- Graft site pain (as applicable)
- Adjacent segment status at 24-months post-operative assessed by quantitative and qualitative radiographic data (translation, angulation, and disc height)

The mean low back pain score over time through the 24-month interval will be summarized using descriptive statistics and a 95% confidence interval based upon the t-distribution. The mean lower extremity (right and left leg) VAS scores over time and the mean ODI score over time will be analyzed in the same manner.

The number and percentage of subjects achieving fusion at the 12-month and 24-month intervals and the corresponding 95% exact (Clopper-Pearson) confidence intervals for the true proportion of subjects achieving fusion will be presented.

The number and percentage of subjects with any device-related serious adverse events (SAEs) and with any study-related adverse events will be presented, together with 95% exact (Clopper-Pearson) confidence intervals for the true proportions. AEs will be summarized at the subject level by type of event using frequencies and percentages. AEs will also be tabulated at the event level by severity and by relatedness.

Neurological status for strength, sensation, and reflexes will be summarized by time point using counts and percentages and 95% exact (Clopper-Pearson) confidence intervals for the true proportions.

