Study-Related Event – An event that meets the definition of an Adverse Event and in addition is determined to have a causal relationship to the study and/or attributable to study participation. The application of a Study-Related Adverse Event status is determined by the Data Monitoring Committee (DMC) as a component of the adjudication process. While all events regardless of status, categorization or relatedness are adjudication by the DMC and reported to FDA, only those events determined to be Study-Related Adverse Events will be included in the final statistical analysis for this trial.

Unknown Related AE – An adverse event that cannot be determined to have a causal relationship with either the investigational device, supplemental fixation hardware or its components, general surgery, or other relatedness.

Unanticipated Adverse Device Effect (UADE) – Any serious adverse effect on health or safety, any life-threatening problem or death caused by, or associated with, a device, if that effect, problem or death was not previously identified in nature, severity or degree of incidence in the application; or any other unanticipated serious problem associated with a device that relates to the rights, safety, or welfare of subjects.

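### The Definitions section limits the final analysis to study-related adverse events, the analysis section plans AE tables without that limit, and no all-cause AE or SAE proportion is planned

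*Combined protocol and SAP*

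**What the plan says.** Section 11.0, in the entry for a study-related event, first says that every event goes to the committee and to FDA, and then sets an analysis rule: "only those events determined to be Study-Related Adverse Events will be included in the final statistical analysis for this trial". The revision history (19.0) lists only the original issue, so this is current text.

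Two other sections describe AE output:

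- Section 2.2 promises "Adverse Event rate(s) reported by relatedness and severity".
- Section 3.2.7 states that "The number and percentage of subjects with any device-related serious adverse events (SAEs) and with any study-related adverse events will be presented", with exact confidence intervals. It then adds that "AEs will be summarized at the subject level by type of event using frequencies and percentages" and that "AEs will also be tabulated at the event level by severity and by relatedness".

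Neither section refers to the rule in 11.0. The outcome list in 3.2.2 names the same two overall safety outcomes as 3.2.7, namely device-related SAEs and study-related AEs.

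The design section (3.1) calls the study a "performance goal investigation designed to evaluate the safety and effectiveness of the SIFS mesh device", with one arm and no control group (3.2.10).

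**The concern.** Someone programming from 3.2.7 and someone programming from 11.0 would build different tables. Section 3.2.7 uses the qualifier study-related for one proportion and drops it for the two tabulations that follow. That suggests the tabulations cover all AEs. Section 11.0 says they do not.

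What is at stake is the safety summary. With no control arm, the reader cannot compare event rates between groups to test whether attribution was sound. Proportions counted regardless of cause are the estimates that do not depend on the committee's causality judgment. The plan names none, and the rule in 11.0 makes that one judgment the condition for an event to enter the final analysis.

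**Working it through.** The point is about text, so the check sets the sections side by side.

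**1. Which events each section covers**

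| Section | Step | Events covered |
|---|---|---|
| 8.0; 11.0 (Adverse Event) | Capture and reporting | All AEs, related or not |
| 9.4 | Committee adjudication of seriousness, relatedness and severity | All AEs |
| 8.2, 8.3 | Seriousness, then severity | Each AE |
| 8.1 | Severity and the device/procedure relatedness class | Study-related AEs |
| 2.2 | AE rates | No limit stated |
| 3.2.7 | By type; by severity and relatedness | No limit stated |
| 11.0 (Study-Related Event) | Final statistical analysis | Study-related AEs only |

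**2. Can 11.0 and 3.2.7 be read together?** Yes, on the narrower reading. Section 8.1 sorts events first into event or non-event, then into study-related or not, and only then assigns a relatedness class. Its classes are device, hardware, procedure, other and unknown; none stands for not study-related. A table by relatedness could therefore be built on the study-related subset alone. Sections 8.2, 8.3 and 9.4 point the other way, because they have every AE adjudicated. The documents do not settle which reading was meant.

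**3. What is missing on each reading**

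- *If 11.0 governs:* AEs, SAEs and deaths judged not study-related appear in no table of the final analysis.
- *If 3.2.7 covers all AEs:* they appear by type, severity and relatedness, but an overall all-cause proportion is still not named. It cannot be rebuilt from what is named. If a share p_j of subjects has an event of type j, the share with any event lies between max(p_j) and the smaller of 1 and the sum of the p_j, because one subject can have several types. Event-level counts give no subject proportion. Nor does 3.2.7 say that the severity table shows seriousness.

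**4. Can all-cause SAEs be tabulated from adjudicated data?** Section 8.1 treats SAE as one of the severity categories and sends study-related AEs to severity adjudication. Read literally, an AE judged not study-related receives no adjudicated seriousness. Sections 8.2, 8.3 and 9.4 say otherwise. The committee charter (Appendix V) was not among the documents reviewed and may resolve this.

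**5. Is the primary analysis touched?** The safety component in 3.2.1, repeated in 3.2.6, is "Freedom from investigational device-related Serious Adverse Events at the index level through the 24-month study interval". A device-related SAE has a causal link to the device, so it is study-related, and the rule in 11.0 removes none of these events. The sample size in 3.2.4 uses a 55% performance goal, a 68% true success rate, one-sided alpha 0.05 and 80% power; no AE rate is a separate input. It reproduces: at n = 87 with success declared at 56 or more, P(X ≥ 56 | p = 0.55) = 0.0487 and P(X ≥ 56 | p = 0.68) = 0.8010, and 87 is the smallest n that reaches 80%.

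**6. Size.** The documents give no AE or SAE rates and no expected share of events judged unrelated, so the number of events the rule would remove cannot be calculated.

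**The case against.** The strongest reply is that nothing is concealed. Section 11.0 states in the same sentence that all events are adjudicated and reported to FDA, and its Adverse Event entry repeats this. Section 3.2.3 provides for subject data listings, 2.2 allows additional parameters to be reported, and 15.0 requires a final report on the whole study experience. The rule in 11.0 is itself stated plainly, and 8.1 offers a way to read the tables consistently with it. All the affected outputs are descriptive.

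Most of this stands, and it rules out three stronger readings that a reader might infer:

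- *That unrelated events are suppressed.* The documents do not support this. Capture, adjudication and FDA reporting are unrestricted; the limit applies to the final statistical analysis.
- *That the sections are in proven contradiction.* They may be, but the adjudication order in 8.1 leaves the narrower reading open. What is certain is that no cross-reference tells the programmer which reading applies.
- *That the rule in 11.0 alone removes a not-study-related row from the relatedness table.* The class list in 8.1 has no such level either.

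The reply does not supply the missing estimate. A listing or an individual event report is not a proportion with a confidence interval, and none of the sections cited names an all-cause one. The charter might settle who adjudicates what, but by the plan's own text 3.2.7 would still lack these rows and 11.0 would still exclude the events.

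**Conclusion.** The concern holds as an inconsistency and an omission in the safety analysis. Section 11.0 restricts the final analysis to study-related AEs, while 2.2 and 3.2.7 plan AE summaries without that restriction. On either reading, no any-AE or any-SAE proportion regardless of cause is planned. If 11.0 governs, an SAE or death judged unrelated is left out of the final analysis of a single-arm trial that is meant to evaluate safety as well as effectiveness. It should be corrected.

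A reader might also infer that the primary result is at risk. On the wording in 3.2.1 and 3.2.6 it is not: the endpoint, its test and the sample size are unaffected. That assurance is limited to this wording, because 2.2 states the safety component more broadly as "Freedom from device-related Serious Adverse Events and secondary surgical interventions at the index level through the 24-month study interval".

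The numerical effect cannot be derived. The conclusion rests on the text alone and assumes that the charter, which was not available, does not change the analysis rule.

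**What to change.** 1. Delete the restriction in the section 11.0 entry for a study-related event.
2. State in 3.2.7 that all AEs and all SAEs in the Treated Population are summarized regardless of relatedness, as the number and percentage of subjects with any AE and with any SAE, each with an exact 95% confidence interval.
3. State that the event-level tables by severity and relatedness include rows for not study-related and for unknown.
4. Show study-related and device-related events as subsets, and leave the two listed safety outcomes unchanged.
5. Align the sentence in 8.1 on severity adjudication with 8.2, 8.3 and 9.4, so that seriousness is adjudicated for every AE, and check that the charter agrees.

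This takes one deletion, one paragraph, one aligned sentence and a few extra tables. It needs no new data collection, because all events are already captured, and no change to the primary endpoint, alpha or sample size. The downside is that reported AE counts will be higher and need explanation, since some of the events will have nothing to do with the device; showing relatedness alongside provides that.

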12.0 PROTOCOL DEVIATION

Deviations from protocol shall be document on a Protocol Deviation (PD) Form. PDs are reportable to the investigator's reviewing IRB and to FDA as a component of the periodic (annual) reporting requirements, unless otherwise directed by the reviewing IRB requirements or as the specific circumstance dictates.

Every attempt shall be made to adhere to the investigation protocol. Should an investigator deviate from the protocol to protect the life or physical wellbeing of a study subject in an emergent circumstance, such notice shall be given to the sponsor as soon as possible, but not more than five (5) working days from the date the emergency occurred. With the exception of the emergent circumstance, prior approval from the study sponsor is required for any change in, or deviation from, the investigation protocol considered to be major as such changes may affect the scientific soundness of the clinical investigation or the rights, safety, and welfare of study subjects.

For reporting purposes, deviations from protocol shall be grouped into the below categories. Examples are provided to ensure consistent reporting.

- *Major Protocol Deviation* – a deviation from the study protocol that impacts the risks and benefits of the study; impacts participant safety, affects the integrity of study data, or affects a participants willingness to participate in the study. For example:
 - Failure to obtain informed consent
 - Informed consent obtained after the study procedure is performed
 - Use of an invalid Informed Consent Form, i.e., consent form without IRB approval stamp, or outdated/expired consent form
 - Enrolling subjects outside the study entrance criteria
 - Failure to perform the final (24-month) study examination/required testing as this impacts the study integrity
- *Minor Protocol Deviation* – a deviation from the study protocol that does not impact participant's safety, compromise the integrity of the study data, or affect participants' willingness to participate in the study. For example:
 - Study visit conducted outside the required timeframe
 - Failure to perform a required interval evaluation – excluding the final (24-month) exam
 - Failure to perform a required research activity

13.0 COMPLIANCE

It is expected that investigational sites (investigators, study coordinators, ancillary site personnel, and subjects) will be compliant with the investigation protocol. Should it be determined that the site is noncompliant, reasonable efforts will be made to secure compliance. These efforts/actions will be documented in writing and maintained within the sponsor study administration file. Should it be determined significant site compliance or site management issues present, these will be documented in a clinical corrective and preventative action (cCAPA) plan. The cCAPA shall define the infraction, outline an action plan to achieve resolution, and be signed by the sponsor representative and the principal investigator at the site. A copy of the signed cCAPA shall be maintained at the investigational site with the original being maintained by the sponsor in the site-specific administrative files.

14.0 INVESTIGATOR RESPONSIBILITY

Investigators are responsible for ensuring the investigation is conducted in accordance with the study protocol and applicable federal regulations (21 CFR, Subpart E). Investigators are additionally responsible for:

- Obtaining IRB approval for study conduct and re-approval as applicable. If more than one (1) investigator at a site is participating in the investigation, the Principal Investigator (PI) shall be responsible for obtaining initial IRB approval and subsequent IRB approvals for the duration of time the site is participating in the trial.
- Obtaining informed consent of study subjects prior to enrollment into the investigation
- Protecting the subject's rights, safety and welfare
- Maintenance of subject records and confidentiality
- Record retention as defined per federal regulations 21 CFR, §812.140 (a), (d), and (e)
- Management of investigation and study related activities in accordance with the Clinical Trial Agreement (CTA)
- Submission of site-specific study closure report to the reviewing IRB within three (3) months of notification from the sponsor. If more than one (1) investigator is participating in the trial at a given site, the PI is responsible for submission of the closure report to the reviewing IRB.
- Return of any unused investigational product to the study sponsor upon request by Spineology or at the conclusion of the investigation.

Note: In the event that an Investigator withdraws from the responsibility to maintain records for the required period of retention required for this investigation, a transfer of custody of records shall be permitted. The transfer of custody must be to an individual willing to accept responsibility for the records in accordance with Federal regulation. Further, a notice of transfer of records shall be provided to FDA no later than 10 working days after the transfer occurs.

15.0 SPONSOR RESPONSIBILITY

The study sponsor, Spineology, is responsible for ensuring the investigation is conducted in accordance with the study protocol and applicable federal regulations, specifically, Title 21 Code of Federal Regulations, Part 812, Part 50, Part 54, Part 56 and Good Clinical Practices (GCPs).

Although included in the above citation, Spineology is additionally responsible for the following:

- Selecting qualified investigators and providing study investigators with appropriate information for study conduct (21 CFR 812.40)
- Ensuing review and approval process for reviewing IRB(s) is obtained (21 CFR 812.40)
- Appropriate monitoring of the clinical investigation (21 CFR 812.46)
- Appropriating reporting in accordance with federal regulation (21 CFR, 812.150(b)(1-10)
- Record maintenance and retention per federal regulation (21 CFR, 812.140 (b)(d) and (e))
- Prompt notification of FDA, IRBs, and all investigators of unanticipated adverse device effects (21 CFR 812.150(b)(1))
- Submission of progress reports in accordance with federal regulation (21 CFR 812.150(b)(5))
- Submission of final study closure report that details the cumulative study experience to FDA, governing IRBs, and Investigators within six (6) months of completing the clinical investigation, in addition to fulfilling semi-annual and annual reporting requirements (21 CFR 812.150(b)(7))

16.0 MONITORING PLAN

This clinical investigation will be monitored by Spineology personnel, or a designated Spineology representative, for appropriate study conduct, compliance and data integrity. In accordance with the Food and Drug Administration's Guidance for Industry, Oversight of Clinical Investigations – A Risk-Based Approach to Monitoring (August 2013) publication, risk-based monitoring practices shall be implemented for the present investigation. Monitoring efforts shall employ periodic on-site monitoring visits and centralized (remote) monitoring that align with Spineology Standard Operating Procedures for clinical site and investigation monitoring.

On-site monitoring shall be conducted to identify data entry errors and discrepancies, missing data, missing data in source records/documents, provide assurance of appropriate source documentation existence, educate sponsor personnel on site-specific procedures, assess site compliance with protocol, and evaluate sites for maintenance or changes in staff, facility, and resources.

Centralized monitoring shall be conducted for remote source data verification, site characteristics and performance metrics to assess for trends, detect high risk type errors and evaluate for other potential risk factors. High risk indicators include, but are not limited to, elements of:

[figure not shown]
- *Protocol Integrity* – randomization/blinding, study entrance criteria, protocol procedure deviation, and lost-to-follow-up.
- *Patient Safety* – adverse events, serious adverse events, unanticipated adverse device effects, inclusion deviations, and informed consent deviation.
- *Regulatory Compliance* – Institutional Review Board approval and investigational device handling/management.
- *Data Quality* – Query resolution, missing data, and missed visit deviations.

For data evaluation, should discrepancies be identified between the comparison of source data and submitted data, data queries will be assigned by the monitor and resolved by the investigational site. Following conclusion of the investigation, Spineology monitors will conduct a site specific study closure visit. The study closure visit will consist of reconciliation of data inconsistencies, outstanding data queries, review of previously unresolved adverse event to either obtain resolution or a current status determination if unable to resolve, and review of administrative materials. In addition, Spineology will perform a device reconciliation of all investigational product ensuring that any and all investigational product that may be at an investigational site is returned to the sponsor. Study closure visits will occur within three (3) months following study conclusion.

Monitoring of this clinical investigation will be accomplished by Spineology, Inc., and performed under the supervision of:

Spineology, Inc.
[name]
[name]

Record retention for this investigation shall be in accordance with Federal regulation (21 CFR §812.140 (a) (b)). Accordingly, Investigator and sponsor investigation records shall be maintained for a period of two (2) years or after the latter of the following two (2) dates:

- The date on which the investigation is terminated or completed, or
- The date that the records are no longer required for purposes of supporting the sponsor's premarket approval application or a notice of completion of a product development protocol.

